**Unblinding:**

Details regarding the unblinding process are available in the unblinding plan (MS200527-0060\_UnblindingPlan\_v2.0\_21Feb2019.pdf)

**Software:**

All statistical analyses will be performed using SAS® (Statistical Analysis System, SAS-Institute, Cary North Carolina, USA, Windows Version 9.4 or higher), or R software (R Foundation for Statistical Computing, Vienna, Austria, Version 3.4.1 or higher) if certain statistical procedures are not available in SAS.

## 10 Trial Subjects

The subsections in this section include specifications for reporting subject disposition and treatment/trial discontinuations. Additionally, procedures for reporting protocol deviations are provided.

### 10.1 Disposition of Subjects and Discontinuations

A table on screened subjects describing the number and percent of subjects in each disposition category will be produced by treatment group. These categories are summarized below:

- Total number of screened subjects, ie subjects that gave informed consent (overall summary only)
- Number of subjects who discontinued prior to randomization and reason (overall summary only)
- Number of randomized subjects
- Number of randomized subjects who did not start treatment
- Number of randomized subjects who permanently discontinued treatment during 12-week treatment period and reason (as reported in the eCRF)
  - Number of randomized subjects who completed safety follow-up period
  - Number of randomized subjects who discontinued from trial during safety follow-up and reason
- Number of randomized subjects who completed 12-week treatment period
  - Number of randomized subjects who completed safety follow-up period
  - Number of randomized subjects who discontinued from trial during safety follow-up and reason
- Number of randomized subjects who signed OLE informed consent under previous versions of the protocol

A table based on screened subjects, describing the number and percent of subjects set by treatment group, will be produced, with the following categories:

- Number of screened subjects
- Number of subjects included in the ITT Analysis Set
- Number of subjects included in the SAF
- Number of subjects included in the mITT Analysis Set
- Number of subjects in MRI Analysis Set
- Number of subjects included in the PP Analysis Set
- Number of subjects included in the MRI PP Analysis Set

- Number of subjects included in the QoL Analysis Set

CCI

- Number of subjects who received at least 1 dose in the OLE under previous versions of the protocol

A table based on screened subjects, describing the number and percent of subjects in each region (Western Europe, US, ROW), country within region, site within country, by analysis set, will be produced.

Another table based on randomized subjects will provide the number and percent of subjects by randomization strata and country. The different randomization strata are listed below:

- MRI substudy participation
  - Yes
  - No
- Region
  - US
  - Western Europe
  - Rest of the world

Corresponding individual listings will be prepared:

- Discontinued subjects (from treatment or study) will be listed with their reason for withdrawal (from treatment or study).
- A listing of the subjects screened but not randomized will be produced with the reason for not being randomized.
- A listing of randomized subjects with subject number, randomization date, and randomized treatment group, ordered by randomization number within randomization stratum, will be produced for the purpose of assessing whether randomization was conducted as planned.
- The list of re-screened subjects and corresponding subject identifiers will be provided. Only the second subject identifier will be used in statistical descriptions and analyses, while the first identifier will not be considered from the disposition counts.

## 10.2 Protocol Deviations

The [Table 6](#) summarizes how protocol deviations will be handled for 12-week treatment period. Protocol deviations in the OLE period will be listed.

**Table 6: Protocol Deviations**

Period covered for protocol deviations reporting	Treatment Group	Observation Period	Analysis Set
12-week treatment period	
 
• Placebo
 
• Evobrutinib 25 mg QD
 
• Evobrutinib 75 mg QD
 
• Evobrutinib 50 mg BID
 
	First dose of 12-week treatment period up to last observed dose during the 12-week treatment, (safety follow-up posterior to the 12-week treatment period included)	ITT

### 10.2.1 Important Protocol Deviations

The following summary tables and listings of important protocol deviations will be provided:

- Tables providing frequency for each type of important protocol deviation/clinically important protocol deviation
- Listing of important protocol deviations

### 10.2.2 Clinically Important Protocol Deviations

Clinically important protocol deviations, as defined in Section 8.1, will be summarized and listed.

For subjects excluded from the PP, the reasons for exclusion will be summarized and listed:

- Frequency table per reason of exclusion from the PP population
- Listing of reasons of exclusion from the PP population

For subjects excluded from the MRI PP, the reasons for exclusion will be summarized and listed:

- Frequency table per reason of exclusion from the MRI PP population
- Listing of reasons of exclusion from the MRI PP population

## 11 Demographics and Other Baseline Characteristics

Demographic and other baseline characteristics will be summarized on mITT and presented by treatment group and overall. All data will also be listed on mITT.

### 11.1 Demographics

The demographic characteristics to be summarized are presented in [Table 7](#).

**Table 7: Demographic Characteristics**

Demographic Characteristics	Modalities
Gender (from DEMO form of eCRF)	
 
• Male,
 
• Female.
 

Race (from DEMO form of eCRF)	
 
• White,
 
• Black or African American,
 
• Asian,
 
• American Indian or Alaska Native,
 
• Native Hawaiian or Other Pacific Islander,
 
• Not collected at this site,
 
• Other.
 

Ethnicity (from DEMO form of eCRF)	
 
• Hispanic or Latino,
 
• Not Hispanic or Latino.
 

Age (defined below)	
 
• < 65 years,
 
• ≥ 65 years.
 

Geographic Region (from IWRS)	
 
• US,
 
• Western Europe,
 
• ROW.
 

European Economic Area (EEA) (from DEMO form of eCRF)	
 
• Yes,
 
• No.
 

Has the subject been enrolled into an MRI site?	
 
• Yes,
 
• No.
 

Is the subject participating in the MRI substudy?	
 
• Yes,
 
• No.
 

Specifications for computation:

- Age (years):
  - $(\text{date of given informed consent} - \text{date of birth} + 1) / 365.25$
  - In case of missing day for the date of birth, but month and year available for both dates:
    - For the derivation of age, the day of birth will be set to 1 and the formula above will be used
  - In case of missing month for the date of birth, but year available for both dates:
    - For the derivation of age, the day and month of birth will be set to 1 and the formula above will be used
- Site codes will be used for the determination of the subject’s geographic region and EEA membership.

## 11.2 Medical History

The medical history will be summarized using Medical Dictionary for Regulatory Activities (MedDRA), current version, PT as event category and MedDRA SOC body term as Body System category. The MedDRA version used will be indicated in footnote. Medical history will be tabulated by SOC and PT. SOC and PT will be alphabetically sorted. Medical history will be also listed.

## 11.3 Other Baseline Characteristics

### 11.3.1 Disease History

Descriptive statistics will be presented for disease history endpoints as indicated in [Table 8](#). The disease history will be repeated for the randomization stratification with marginal total for each category of MRI substudy participation and Region by treatment group.

**Table 8: Disease History**

Disease History Characteristics	Modalities
Time (months) since confirmed diagnosis of RA according to 2010 ACR/The EULAR RA classification criteria.	
 
• Summary statistics will be presented.
 
• Time will be computed as <math>(\text{Date of Informed Consent Signature} - \text{Date of confirmed diagnosis of RA}) / 30.4375</math>. If the date of confirmed diagnosis of RA is entirely missing, then time since confirmed diagnosis of RA will not be computed. In case of partial missing date of confirmed diagnosis of RA, this date will be imputed as follows:               
 
○ If only the day is missing, then it will be replaced by the first day of the month
 
○ If both day and month are missing, then it will be replaced by the first of January
 
 
 

Components from the ACR Core Set:
 
 
• Tender Joint Count ([TJC] among the 68-joint count),
 
• Swollen Joint Count ([SJC] among the 66-joint count),
 
• Subject's Global Assessment of Disease Activity (100-mm VAS),
 
• Subject's Assessment of Pain (100-mm VAS),
 
• HAQ-DI total score,
 
• Physician's Global Assessment of Disease Activity (100-mm VAS),
 
• hsCRP (mg/L)
 
	
 
• Summary statistics
 

Erythrocyte sedimentation rate (ESR) (mm/Hr)
	
By category (based on local normal ranges collected in electronic case report form [eCRF]):
 
 
• Low
 
• Normal
 
• High
 

hsCRP (mg/L)
	
By category:
 
 
• Normal
 
• High
 

Acute-phase reactant
	
At least one test result is needed for the classification:
 
 
• Normal hsCRP and normal ESR,
 
• Abnormal hsCRP or abnormal ESR
 
 
Abnormal refers to either low or high normal range classification.

Rheumatoid factor (RF) (expressed in IU/mL)
	
By category:
 
 
• Negative (<math>\leq</math> Upper Limit of Normal [ULN])
 
• Positive (<math>></math> ULN)
 

Serum Ig levels (IgG, IgA, IgM) (mg/dL)
	
By category:
 
 
• Negative (<math>\leq</math> ULN)
 
• Positive (<math>></math> ULN)
 


Anti-cyclic citrullinated peptide (Anti-CCP) (Units)
	
By category:
 
 
• Negative (<math>\leq</math> ULN)
 
• Positive (<math>></math> ULN)
 

Serology
	
By category (At least one test result is needed for the classification):
 
 
• Negative RF and negative anti-CCP (<math>\leq</math> ULN),
 
• Low-positive RF or low-positive anti-CCP (<math>></math> ULN, <math>\leq 3*ULN</math>),
 
• High-positive RF or high positive anti-CCP (<math>></math> <math>3*ULN</math>)
 
• Missing RF and missing anti-CCP
 

14-3-3η (ng/mL)	By category: 
 
• Negative (≤ ULN)
 
• Positive (> ULN)
 

DAS28-hsCRP (See Appendix 18.1 for definition)	By category: 
 
• < 2.6 [remission],
 
• ≥ 2.6 to < 3.2 [low],
 
• ≥ 3.2 to ≤ 5.1 [moderate],
 
• > 5.1 [high].
 

CDAI (See Appendix 18.1 for definition)	By category: 
 
• ≤ 2.8 [remission],
 
• > 2.8 to ≤ 10.0 [low],
 
• > 10.0 to ≤ 22.0 [moderate],
 
• > 22.0 [high].
 

SDAI (See Appendix 18.1 for definition)	By category: 
 
• ≤ 3.3 [remission],
 
• > 3.3 to ≤ 11.0 [low],
 
• > 11.0 to ≤ 26.0 [moderate],
 
• > 26.0 [high].
 

EULAR/ACR Boolean Remission (See Appendix 18.1 for definition)	
 
• Yes,
 
• No.
 

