### 5.5.1.1 Stopping Rules

The severity of AEs will be graded using the NCI-Common Terminology Criteria for Adverse Events (CTCAE) v4.03 grading scale ([Hahn 2012](#)).

The IMP should be temporarily withheld or permanently withdrawn if the following abnormalities occur or re-occur, as relevant, and re-initiation following temporarily withholding of IMP should be discussed with the Medical Monitor. If a subject's predose baseline value falls within any of the below criteria, consult with the Medical Monitor regarding potential withdrawal, continued participation in study, and additional monitoring if needed:

- For a neutrophil count  $< 500/\text{mm}^3$  or platelet count  $< 25,000/\text{mm}^3$  or lymphocyte count  $< 200/\text{mm}^3$  (Grade 4) or neutrophil count 500 to  $999/\text{mm}^3$  (Grade 3) with fever or platelet count 25,000 to  $49,999/\text{mm}^3$  (Grade 3) with bleeding, the IMP should be permanently withdrawn.
  - For a Grade 3 decrease in neutrophil count without fever or Grade 3 decrease in platelet count without bleeding, temporarily hold the IMP and recheck the value. If the value is still Grade 3, permanently discontinue the IMP.
  - For a decrease to Grade 2, temporarily hold the IMP and recheck the value. Discontinue the IMP if the neutrophil or platelet count continues to decrease, and re-initiate the IMP if no downward trend is observed.

The image shows the letters 'CCI' in a large, bold, red font. The 'C's are stylized with a gap at the top, and the 'I' is a simple vertical bar. The text is centered on a solid black rectangular background.

- For an increase in serum creatinine to  $> 3 \times$  Baseline (Grade 3 or higher), the IMP should be permanently withdrawn.
  - For any other increase in serum creatinine  $> 1.5 \times$  Baseline, temporarily hold the IMP and recheck the value. Discontinue the IMP if the value does not decrease, or re-initiate the IMP if a downward trend is observed.
- For any serum IgG level  $< 3$  g/L, confirmed by repeat testing, the IMP should be permanently withdrawn.

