## 15.8 Serum IgG, IgA, IgM Levels

Boxplot of Serum IgG, IgA and IgM levels (mg/dL) by treatment group and time point will be provided. Descriptive statistics by treatment group and time point will be performed as well. Serum IgG, IgA and IgM levels data will be listed by treatment group, subject and time point (where applicable).

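### Serum immunoglobulin is categorised only against the upper limit at baseline, and no visible summary table counts subjects with low values on treatment

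*SAP*

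**What the plan says.** **Baseline.** SAP section 11 states that "Demographic and other baseline characteristics will be summarized on mITT and presented by treatment group and overall". Within it, Table 8 (Disease History) has a row "Serum Ig levels (IgG, IgA, IgM) (mg/dL"), shown by category only: Negative at or below ULN, Positive above ULN. The RF, anti-CCP and 14-3-3η rows use the same labels and the same cut. The ESR row of the same table has Low, Normal and High.

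**On treatment.** SAP section 15.8 plans boxplots in mg/dL by arm and time point and subject listings, and adds: "Descriptive statistics by treatment group and time point will be performed as well". It plans no categories.

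**Stopping rule.** Protocol section 5.5.1.1 says that for a serum IgG below 3 g/L, "confirmed by repeat testing, the IMP should be permanently withdrawn". The introduction to those rules also provides for a subject whose "predose baseline value falls within any of the below criteria"; the Medical Monitor is then consulted.

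**Status of the endpoint.** Protocol section 8.3.2 lists serum IgG, IgA and IgM among the key secondary safety endpoints. Section 3.4 names infection as an important potential risk tied to the drug's immunomodulatory action.

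**The concern.** Negative and Positive are natural labels for an autoantibody test, where only a raised result is informative. Total immunoglobulins are quantities with a lower and an upper limit, and the only immunoglobulin rule visible in the protocol looks at the lower side. The Table 8 split therefore separates subjects in the direction the protocol does not act on, and merges them in the direction it does.

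The second gap is independent of the first. After baseline, a safety reader will want to know how many subjects in each arm fell below normal, and how many fell below the level at which the protocol withdraws treatment. No visible summary table gives either number. Without them, arms can be compared on typical immunoglobulin levels but not directly on how often low values occurred.

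**Working it through.** No sample size, power or alpha figure is involved. The check sets the provisions side by side, with three short pieces of arithmetic.

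**1. The baseline rule.** For a value x, Table 8 assigns Negative if x ≤ ULN and Positive if x > ULN. Because LLN < ULN, every x < LLN also satisfies x ≤ ULN. So all low values, 100% of them, are labelled Negative together with the normal ones. The documents give no reference ranges and the argument needs none.

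**2. The unit.** 3 g/L = 3 × 1000 mg per 10 dL = 300 mg/dL. The SAP shows immunoglobulin in mg/dL, so the protocol's threshold is 300 on the SAP's scale. SAP section 15.3 says laboratory results will be presented in SI units.

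**3. What the SAP plans for parameters named in the visible stopping rules.**

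| Parameter (Protocol 5.5.1.1) | Categorical summary in the SAP |
|---|---|
| Neutrophils, platelets, lymphocytes | Shift table by worst CTCAE grade, hematology (15.3, Table 53) |
| Creatinine | Shift table by worst CTCAE grade, biochemistry (15.3, Table 53) |
| HBV DNA | Shift table, baseline to worst, below 20 against 20 IU/mL or more (15.11) |
| IgG | None visible (15.8); immunoglobulins are not in Table 53 |

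The HBV DNA cut at 20 IU/mL matches one limb of the protocol's HBV stopping rule. Among the parameters named in the visible rules, IgG is the one without a categorical table.

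**4. Can the count be recovered from the planned statistics?** SAP section 9.4 includes Q1, Q3, minimum and maximum. Take one visit with all 90 planned subjects of an arm measured (an assumption; fewer subjects narrow the range). 90/4 = 22.5, so the first quartile is the 23rd smallest value. Let k be the number of subjects below 300 mg/dL. The minimum is below 300 whenever k ≥ 1. The first quartile is at or above 300 whenever k ≤ 22. A table with a minimum below 300 and a first quartile at or above 300 is therefore consistent with any k from 1 to 22, that is 1/90 = 1.1% to 22/90 = 24.4%. This is the range left open by those two statistics, not a forecast. Because the statistics are given visit by visit, they also do not show how many different subjects were low at any time.

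**The case against.** Four objections carry weight.

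- **Table 8 does not govern the on-treatment analysis.** A reader might infer that its ULN split causes low values to be pooled with normal ones throughout. The documents do not support that: Table 8 is a baseline table, and section 15.8 works on the continuous scale with no split.
- **Low values are visible.** A reader might infer that low immunoglobulin is never counted anywhere. That goes too far. Minima, first quartiles, boxplots and listings would all show it. Under Protocol section 7.4.1.1, a laboratory abnormality leading to discontinuation is reported as an adverse event, and SAP Table 25 tabulates treatment-emergent events leading to withdrawal. A subject withdrawn for low IgG would be counted there, though not necessarily under a dedicated low-IgG row.
- **Entry may already screen out low IgG.** A reader might infer that nothing prevents such a subject from entering. Immunoglobulins are measured at Screening, exclusion 30 covers other clinically significant laboratory abnormalities, and exclusion 15 is redacted.
- **The SAP breaks no commitment.** Protocol section 8.5.4.1 asks for summary statistics of continuous laboratory parameters and reserves shift tables for categorical ones.

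All four narrow the point, but none removes it. A minimum identifies one value, not a number of subjects. The adverse-event route misses low baseline values and symptomless falls that neither stop treatment nor are judged medically important. Boxplot points and listings allow a hand count, but the SAP does not plan to report one.

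**Conclusion.** The point holds in two separate parts. At baseline, the stated category rule puts every low immunoglobulin in the same class as normal. On treatment, no visible summary table counts subjects per arm below LLN or below the protocol's 3 g/L for IgG, although the SAP supplies the equivalent for HBV DNA.

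The size is moderate: a reporting gap on a key secondary safety endpoint, with no effect on the primary or key secondary efficacy analyses. How many subjects would be affected cannot be estimated from the documents.

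Two limits apply. The visible stopping rule covers IgG only, so it should not be read as extending to IgA or IgM; for those, the case rests on LLN alone. The text on adverse events of special interest is redacted and Appendix 18.10 (Tier 1 events) is not available here, so a low-immunoglobulin category in either cannot be excluded. The 3 g/L threshold is taken as the protocol states it; nothing here bears on whether it is the right clinical limit.

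**What to change.** In SAP Table 8, replace Negative/Positive for IgG, IgA and IgM with Low (below LLN), Normal and High (above ULN).

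In SAP section 15.8, add a by-arm shift table from baseline category to lowest post-baseline category for IgG, IgA and IgM, with a further IgG category at the protocol's existing 3 g/L. Present immunoglobulins in g/L, in line with the SI-unit rule in section 15.3, so that the threshold can be read directly.

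The cost is a wording change to one row, a unit change and one extra table. The immunoglobulin values are already collected. No clinical rule changes.

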### 11.3.2 Other

Chest X-ray evaluations will be listed and tabulated by treatment group using the number and percentage of subjects for each interpretation category (Normal, Abnormal Not Clinically Significant, Clinically Significant, and Abnormal Overall).

Other characteristics like viral serology, Quantiferon TB test, thyroid-stimulating hormone and prior surgeries will be listed only.

## 12 Previous or Concomitant Medications/Procedures

Previous or concomitant medications during the 12 weeks treatment period will be summarized using the SAF.

As detailed in Section 7, some subjects have entered in the OLE, even if the Sponsor decided not to initiate the OLE in protocol V3.0. Therefore, concomitant medications during OLE will also be summarized for subjects who received at least 1 dose in the OLE under previous versions of the protocol.

The definition of previous or concomitant medications is presented in [Table 9](#):

**Table 9: Definition of Previous/Concomitant Medications**

Analysis Set	Period covered	Treatment groups	Definition
SAF	12-week treatment period	
 
• Placebo
 
• Evobrutinib 25 mg QD
 
• Evobrutinib 75 mg QD
 
• Evobrutinib 50 mg BID
 
	
Previous medications are medications, other than trial medications, which either:
 
 
1. started and stopped before first administration of any IMP (placebo or evobrutinib) or
 
2. started prior to the first administration of IMP (placebo or evobrutinib) and are taken by subjects on or after the first administration of IMP.
 

			
Concomitant medications are medications, other than IMPs, which either:
 
 
1. started on or after the first administration of any IMP (placebo or evobrutinib) or
 
2. started prior to the first administration of IMP (placebo or evobrutinib) and are taken by subjects on or after the first administration of IMP.
 

Subjects with at least 1 dose during OLE	OLE	
 
• Placebo/Evobrutinib 50 mg BID
 
• Evobrutinib 25 mg QD/Evobrutinib 50 mg BID
 
• Evobrutinib 75 mg QD/Evobrutinib 50 mg BID
 
• Evobrutinib 50 mg BID/Evobrutinib 50 mg BID
 
	
Concomitant medications are medications, other than IMPs, which either:
 
 
1. started on or after the first administration of evobrutinib during OLE or
 
2. started prior the first administration of evobrutinib during OLE and are taken by subjects on or after the first administration of evobrutinib during OLE.
 

Partial dates will be handled as follows:

- For previous medications, in case the date values will not allow a medication to be unequivocally allocated to previous medication, the medication will be considered as previous medication.
- For concomitant medications, in case the date values will not allow a medication to be unequivocally allocated to concomitant medication, the medication will be considered as concomitant medication.

The ATC-2nd level and PT will be tabulated as given from the World Health Organization Drug Dictionary (WHO-DD) current version. In case multiple ATCs are assigned to a drug, all ATC2nd level will be used for reporting.

The number and proportion of subjects with previous or concomitant medications (previous medications will not be summarized for final analysis) will be separately summarized by treatment group and will be presented by descending frequency of ATC 2nd level term and then by descending frequency of PT in total column. If multiple ATCs/PTs have the same frequency, they will be sorted alphabetically. The WHO-DD version used will be indicated in footnote.

Previous or concomitant medications will be also listed.

All concurrent procedures, which were undertaken any time on trial, will be summarized. Number of subjects with concurrent procedures (prior, on or after the first day of IMP) overall and by SOC and PT will be summarized by treatment group, using current version of MedDRA dictionary.

Concurrent procedures will be also listed.

